#### Swallowing Effort:

Both swallowing amplitude and timing parameters will be obtained by analyzing the individual graphic waveforms produced by the DSW algorithm. Measures will be obtained for each of the 8 swallows, at each of the HFNC flow rates.

### **Procedures Done for Research Purpose**

- The use of HFNC with three levels of flow (30, 45, and 60 L/min or 30, 45, and 50 L/min [for small-size nasal prongs]).
- Swallow frequency measurement through sEMG.

Swallowing effort measurement through sEMG – participants will swallow measured amounts of water and applesauce. Presentation of the different volumes and viscosities will be done in pre-determined random order.

**Application of sEMG monitor**

- Patient sits quietly for 10 minutes to establish baseline swallow frequency

- Participants swallow 8 boluses to establish baseline swallow effort
- Two trials of water at two volumes (5 and 10 ml)
- Two trials of applesauce at two volumes (5 and 10 ml)
- Participants will rest for 15 seconds after completing each swallow

Participants placed on HFNC cannula (size based on manufacturer recommendations)

HFNC flowrate applied to patient at random amounts for 15 mins per flowrate

- For each flowrate, swallow frequency will be recorded for the first 10 minutes. During the last 5 minutes, the participants will complete the 8 aforementioned swallows (water and applesauce)
- After swallows are complete for each flowrate, the HFNC will be removed and participant will rest for 10 minutes
- After the rest period, the process will be repeated with the other flowrates (random order)

## Subject Population

Fifty healthy adult volunteers above the age of 21 will be assessed.

Inclusion criteria:

- Age >21 y/o
- Functional cognition as determined by the participant's ability to follow verbal directions; no formal cognitive test will be administered. Anyone not able to follow 1-step directions will be withdrawn from the study.
- Eat a “general/regular consistency” diet—determined by scoring a 6 or 7 on the Functional Oral Intake Scale (FOIS).

Exclusion criteria:

- Age < 21 y/o
- Allergy to applesauce
- History of dysphagia or disease/condition that may cause dysphagia such as:
  - Achalasia
  - Diffuse spasm
  - Esophageal tumors or scar tissue
  - Esophageal rings
  - Gastroesophageal reflux disease (GERD)
  - Eosinophilic esophagitis
  - Scleroderma
  - Radiation therapy
  - Neurological disorders (multiple sclerosis, muscular dystrophy and Parkinson's disease)
  - Neurological damage (from a stroke or brain or spinal cord injury)
  - Pharyngeal diverticula
- Use of medications that alter swallowing function
  - Benztropine mesylate (Cogentin)
  - Oxybutynin (Ditropan)

- Propantheline (Pro-Banthine)
- Tolterodine (Detrol)
- The presence of tracheostomy tube.
- Nasal obstruction.

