## **Experimental Design and methods**

This is a prospective study designed to measure swallowing frequency and swallowing effort in fifty healthy adult volunteers (25 participants will be between 21 and 49 years old; and the other 25 above 50 years old). To recruit volunteer participants, an email will be sent via university internal email system to the faculty, students and employees in the departments of Respiratory Care and Speech Language Pathology. Snowball sampling (non-probability sampling) will also be utilized to recruit individuals outside of those departments. No compensation is offered to the participants. Enrolled participants are sub-categorized into two different age groups to

determine if there are any swallowing differences between the different age groups. Inclusion criteria include individuals who are older than 21 years of age and have no cognitive impairment. Exclusion criteria include individuals who are less than 21 years of age, have a history of dysphagia or disease/condition that may cause dysphagia, current use of medications that alter swallowing function, nasal obstruction, and the presence of a tracheostomy tube.

Upon meeting inclusion criteria, informed consent explaining the procedure and potential harm will be obtained and a copy will be given to the subject. Then, a unique identification code number will be assigned to protect the subject's identity.

HFNC:

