The AIRVO 2 high-flow nasal cannula system (Fisher and Paykel Healthcare Limited, Panmure, Auckland, New Zealand) will be used. Nasal prongs sizes are chosen as per manufacturer recommendations. Participants will receive three levels of HFNC flow rates (30, 45, and 60 L/min) through nasal prongs. If a small-size nasal prong is used, the participant will receive 30, 45, and 50 L/min flow rates instead of 30, 45, and 60 L/min, as manufacturer recommendations state the maximum liter flow for a small-size nasal prong is 50 L/min. Oxygen concentration will be set at 21% and a temperature of 37 °C. First, individuals will be placed on the sEMG monitor. Following the application of the sEMG, each participant will sit quietly for 10 minutes, before being attached to the HFNC, so a baseline swallow frequency can be established. After the baseline swallow frequency is established, each participant will be asked to swallow 8 boluses: 2 trials of water at 2 volumes (5 and 10 mL) and 2 trials of applesauce at 2 volumes (5 and 10 mL). Participants will rest for 15 seconds after completing each swallow. This procedure will establish the participant's baseline swallowing effort measurements. Once these swallows have been completed, the participant will be placed on the HFNC. Each participant will be placed on three different flow rates (30, 45, and 60 L/min or 30, 45, and 50 L/min) in random order. The random order will be generated by an online random number tool (<https://www.randomizer.org>). The study participant will be subjected to each flow rate for 15 minutes. During the first 10 minutes, swallow frequency will be recorded. After 10 minutes at the given flow, the participant will complete the 8 aforementioned swallows. After completing all of the swallowing trials, the participant will be removed from the HFNC for a period of 10 minutes. This process will be repeated for all three

flowrates for a total of 32 boluses swallowed.

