#### Swallowing Frequency:

Swallowing frequency is analyzed by sEMG signals recorded on the KayPentax Digital Swallow Workstation™ with integrated digital swallowing signals lab (DSW™, Model 7120, New Jersey). A three-sensor sEMG electrode (Uni-Patch™, Disk #7500, Covidien Corporation, Tyco Healthcare, Wabasha, MN) will be placed on the anterior neck skin under the chin, over the submental muscles above the hyoid bone. Each patch will include two recording electrodes and a third ground electrode. Spontaneous swallowing frequency is calculated as the number of swallows per minute (SPM) for 10 minutes on room air and then for each HFNC intervention. Swallows will be counted from the visual myographic waveform produced by the DSW.

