### **Recruitment and Consent Procedures:**

- Recruitment will be based on the inclusion and exclusion criteria.
- Emails will be used to inform potential participants.
- Snowball sampling (non-probability sampling) will be utilized to recruit individuals outside of the Respiratory Care and Speech Language departments
- Informed consent explaining the procedures and potential harm will be obtained from all individual participants in the study.

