### **Risk to subject:**

- Risks include aspiration of water or applesauce when swallowing on the HFNC. Discomfort and dryness of mouth or nose due to the use of the high flow. Also, since the swallowing measurement device is applied through patch to skin, allergic reaction may occur. Participants will be closely monitored by the study investigators and if any signs of aspiration (coughing, shortness of breath), discomfort, or allergic reaction occurs, the session will be terminated and the participant will be withdrawn from the study.

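### Allergic reaction to the sEMG skin patch is a named risk, but neither exclusion list covers a known patch or electrode reaction, so such a volunteer is eligible and would be exposed if they consent (minor)

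*Combined protocol and SAP*

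**What the plan says.** The combined protocol and SAP deals with allergy in three places, and they do not line up.

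- **Risk to subject** identifies the patch as the source of a possible reaction: "since the swallowing measurement device is applied through patch to skin, allergic reaction may occur". If "discomfort, or allergic reaction occurs, the session will be terminated and the participant will be withdrawn from the study".
- **Subject Population** has one allergy exclusion: "Allergy to applesauce".
- **Experimental Design and methods** gives a second, narrative list, beginning "Exclusion criteria include individuals who are less than 21 years of age, have a history of dysphagia or disease/condition that may cause dysphagia". It continues with medications that affect swallowing, nasal obstruction and tracheostomy. It has no allergy criterion of any kind, not even applesauce.

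Exposure is universal. In the procedure, "First, individuals will be placed on the sEMG monitor", before any measurement is taken. Under Swallowing Frequency, the electrode "will be placed on the anterior neck skin under the chin, over the submental muscles above the hyoid bone".

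On enrolment, Recruitment and Consent Procedures states: "Recruitment will be based on the inclusion and exclusion criteria". The same section, and Experimental Design and methods, require informed consent that explains the procedures and the potential harm.

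**The concern.** The authors accepted that a known allergy to a study material can be a reason not to enrol someone, and applied this to applesauce. For the patch, the one material to which the risk section ties an allergic reaction, they wrote no matching criterion. A person who already knows that they react to skin patches or electrodes passes both lists.

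Two things are at stake. The first is an avoidable exposure of healthy, unpaid volunteers to a harm that the protocol itself foresees. The second is data. The sEMG signal is the only source of all three outcomes (swallowing frequency, amplitude and timing), so a session stopped for a reaction leaves the remaining flow conditions unmeasured in a design that compares conditions within each person.

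**Working it through.** The plan states no figure on this point, so there is none to reproduce. The check is mainly a comparison of the text.

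**1. Named risk against the eligibility lists**

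| Item | Risk to subject | Subject Population exclusions | Narrative exclusions (Experimental Design and methods) |
|---|---|---|---|
| Allergic reaction to patch | Named | Absent | Absent |
| Applesauce allergy | Not named as such | Present | Absent |

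No section mentions an exclusion or screening question for adhesive, electrode, latex or skin sensitivity. The two lists also disagree with each other on applesauce.

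**2. Does a volunteer with a known patch reaction qualify?** Recruitment is tied to the inclusion and exclusion criteria. Such a person can meet the age, cognition and diet criteria and match no exclusion. They are eligible as written.

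**3. Would they be exposed?** Only if they consent. Consent is obtained before the monitor is applied and is meant to explain potential harm, so they may decline or raise the matter. If they go ahead, the patch is applied first.

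**4. How long is the contact?** From the procedure:
- baseline frequency recording, 10 min;
- baseline set of 8 swallows, taken as 5 min (an assumption, borrowed from the 5 min that the procedure outline allows for the same set at each flow rate);
- three flow rates, 3 × 15 = 45 min;
- rests of 10 min each, 2 or 3 depending on whether the one after the last flow rate is counted, so 20 to 30 min.

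The total is 10 + 5 + 45 + 20 = 80 min to 10 + 5 + 45 + 30 = 90 min, assuming that the patch stays on during the rests. Contact is not momentary.

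**5. What do the existing safeguards do?** Consent works through the volunteer's own choice and sets no eligibility rule. Monitoring, termination and withdrawal work only once a reaction has begun.

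**6. What does a withdrawal cost the analysis?** Plans for Data Analysis specifies a one-way and a four-way repeated-measures ANOVA and gives no rule for incomplete participants or for replacement. One withdrawal is 1/50 = 2% of the sample, or 1/25 = 4% of an age group. How many withdrawals the gap would cause cannot be derived from the documents.

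**The case against.** The strongest reply is that the protocol already handles this risk. It names it, discloses it through consent, monitors for it, and ends the session if it occurs. Volunteers are unpaid, and many will come from respiratory care and speech-language departments, so someone with a known reaction would probably speak up. Nor does every named risk need an exclusion: dryness of the mouth or nose is also listed, without one.

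Much of this stands, and it limits the severity. It does not close the gap. Consent leaves the person eligible, and the later safeguards follow exposure. Dryness is not a good parallel: it is an effect of the flow, whereas a previous patch reaction is history that one question can elicit, and the plan already treats applesauce allergy in that way.

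A reader might infer several stronger things that the documents do not support:

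- **That sites would enrol, expose and then withdraw such a person.** Consent comes in between. The consent pages are not in the copy under review, so a screening question there cannot be ruled out. The documents show only that the eligibility criteria omit one.
- **That both lists screen for food allergy.** Only Subject Population does.
- **That the protocol names an adhesive allergy.** It speaks of a patch on the skin; adhesive and gel are reasonable inferences about its materials.
- **That the chance of enrolling an affected person can be quantified.** Assuming a prevalence of 1% to 5% gives 1 − 0.99^50 = 39% to 1 − 0.95^50 = 92% for at least one in 50, and 0.5 to 2.5 people expected. Nothing in the documents supports that prevalence. The calculation also assumes that nobody with a known reaction declines, and it says nothing about how many would react to this electrode.

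**Conclusion.** The gap is real and minor. As written, a known reaction to skin patches or electrodes does not exclude a volunteer, although the protocol names allergic reaction to the patch as a risk and every participant wears it. The person would be exposed if they consent; disclosure makes that less likely without ruling it out. If a reaction occurs, withdrawal loses the rest of that person's sEMG data.

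The conclusion rests on the two eligibility lists being complete as shown, and they bear no sign of a cut or redaction. It does not depend on any assumed prevalence. With no prevalence or reaction rate in the documents, the size of the benefit is unknown. No hypothesis test or stated figure changes. The case for acting is that the improvement in safety costs very little.

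**What to change.** - Add to the exclusion criteria in both Subject Population and Experimental Design and methods: a known allergy or previous skin reaction to the electrode patch or its materials (for example medical adhesive or electrode gel).
- Ask about this once, at screening, before the patch is applied.
- Carry the applesauce exclusion into the narrative list in Experimental Design and methods, so that the two lists agree with each other and with the risk section.

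The cost is one line in each list and one screening question. The downside is that perhaps one or two volunteers are turned away and replaced before enrolment. That number is a guess, since the documents give no prevalence.

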### **Recruitment and Consent Procedures:**

- Recruitment will be based on the inclusion and exclusion criteria.
- Emails will be used to inform potential participants.
- Snowball sampling (non-probability sampling) will be utilized to recruit individuals outside of the Respiratory Care and Speech Language departments
- Informed consent explaining the procedures and potential harm will be obtained from all individual participants in the study.

### **Compensation:**

- There will be no compensation provided to participants for participation in this study.

### **Risk to subject:**

- Risks include aspiration of water or applesauce when swallowing on the HFNC. Discomfort and dryness of mouth or nose due to the use of the high flow. Also, since the swallowing measurement device is applied through patch to skin, allergic reaction may occur. Participants will be closely monitored by the study investigators and if any signs of aspiration (coughing, shortness of breath), discomfort, or allergic reaction occurs, the session will be terminated and the participant will be withdrawn from the study.

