**Plans for Data Analysis:**

- The data collected will include swallow frequency (calculated as swallows per minute), peak effort amplitude (the highest amplitude of swallowing effort), and swallowing speed (the difference between the onset and offset of muscle contraction). Simple 1-way repeated measures ANOVA will be used to determine significant differences in swallowing frequency between oxygen flow rates ( $p < .05$ ). A 4-way mixed methods repeated measures ANOVA (HFNC x volume x viscosity x age) will be used to determine significant differences in amplitude and timing ( $p < .05$ ).

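### Participants are withdrawn for events the plan links to high flow, but the repeated-measures ANOVAs have no rule for their partial data and no count of terminations by flow is planned

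*Combined protocol and SAP*

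**What the plan says.** The Risk to subject section states that "if any signs of aspiration (coughing, shortness of breath), discomfort, or allergic reaction occurs, the session will be terminated"; the consequence is that "the session will be terminated and the participant will be withdrawn from the study". Two of the triggers are tied there to the intervention: "Risks include aspiration of water or applesauce when swallowing on the HFNC" and "Discomfort and dryness of mouth or nose due to the use of the high flow". Allergic reaction is tied to the electrode patch, not to flow.

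The outcomes are defined at every flow. Frequency is "the number of swallows per minute (SPM) for 10 minutes on room air and then for each HFNC intervention". For amplitude and timing, "Measures will be obtained for each of the 8 swallows, at each of the HFNC flow rates".

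Plans for Data Analysis gives two methods. For frequency, "Simple 1-way repeated measures ANOVA will be used to determine significant differences in swallowing frequency between oxygen flow rates". For amplitude and timing, "A 4-way mixed methods repeated measures ANOVA (HFNC x volume x viscosity x age) will be used". The data items listed there are frequency, peak amplitude and speed. No section defines an analysis set, a rule for partial data, a rule for a frequency recording that is cut short, replacement of withdrawn participants, or a table of terminations.

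**The concern.** A conventional repeated-measures ANOVA needs a value in every within-subject cell. A participant stopped at one flow would ordinarily be dropped whole, including baseline and any flows already completed. Flow order is random, so a stop at the highest flow can come first and also remove the lower flows.

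Coughing on a bolus and discomfort are plausible effects of the exposure under test, so the missing values may be related to the response. The flow comparison would then lean towards people who tolerated HFNC. If the analyst instead keeps partial records, that choice is made after the data are seen. Either way, the flow at which people had to stop bears directly on the study's aim, and the plan does not provide for tabulating it.

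**Working it through.** **No planned figure to reproduce.** The documents give no withdrawal rate, effect size, SD or sample-size calculation. Every risk and correlation below is an assumption.

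**Inputs from the documents.** 50 healthy adults. Three flows in random order. At each flow, a 10-minute frequency recording followed by 8 boluses (two trials of each of four volume-by-viscosity types, in random order). On-flow boluses: 3 × 8 = 24.

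**Who is lost after a cough stop.** Frequency at a flow is recorded before its boluses. A stop during the boluses of the first or second flow (16 boluses) removes later frequency recordings. A stop during the third flow's boluses leaves frequency complete, and leaves amplitude and timing complete if each of the four bolus types has already been recorded at least once. That last step assumes the two trials are averaged and the provoking swallow is not recorded. The chance that all four types are covered after k swallows, c(k), is:
- k below 4: 0
- k = 4: 16/70 = 0.229
- k = 5: 32/56 = 0.571
- k = 6: 24/28 = 0.857
- k = 7: 1

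**Equal cough risk p per bolus for everyone.**
- Withdrawn: 1 − (1 − p)^24
- Out of the frequency ANOVA: 1 − (1 − p)^16
- Out of the 4-way ANOVA: 1 − (1 − p)^16 + (1 − p)^16 × Σ over k = 0 to 7 of (1 − p)^k × p × [1 − c(k)]

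| p | Withdrawn | Frequency | Amplitude and timing |
|---|---|---|---|
| 0.1% | 2.4% | 1.6% | 2.1% |
| 0.25% | 5.8% | 3.9% | 5.2% |
| 0.5% | 11.3% | 7.7% | 10.1% |
| 1% | 21.4% | 14.9% | 19.3% |

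Of 50 people, that is about 1 to 7 out of the frequency ANOVA and 1 to 10 out of the other. Interval widening is roughly 1/√(1 − e), where e is the excluded fraction: 1.008 to 1.084 for frequency and 1.011 to 1.113 for amplitude and timing, so about 1% to 11% from cough stops alone. With equal risk there is no selection between persons.

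**Same mean risk held by 10% of people (10p each).** The fraction excluded is 0.1 times the formulas above evaluated at 10p. For example, frequency at p = 1% is 0.1 × (1 − 0.9^16) = 8.1%. The ranges are 1.5% to 8.1% (frequency) and 1.9% to 8.9% (amplitude and timing).

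**Bias under this person-level version.** Let rho be the correlation between a person's flow effect and a latent normal tendency to be excluded. The completer mean shifts by |rho| × φ(z)/(1 − e), where z is the (1 − e) normal quantile, in SDs of the person-level effect.
- Frequency: φ(z)/(1 − e) is 0.038 at e = 1.5% and 0.164 at e = 8.1%.
- Amplitude and timing: 0.048 at e = 1.9% and 0.177 at e = 8.9%.
- At |rho| = 0.3, both give about 0.01 to 0.05 SD. The shift is zero at rho = 0 and can go in either direction.

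**Discomfort, taken separately.** If the chance that discomfort stops the 10-minute recording is 1% to 5% per flow and a shortened recording is not used, 1 − (1 − d)^3 gives 3.0% to 14.3% excluded from both analyses. This has not been combined with cough, so the cough figures are not the total loss.

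**The case against.** Several points on the other side stand.

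- A reader might infer that the results would describe only people who tolerated all three flows. The documents do not support that. Exclusion is not a written rule, and a third-flow bolus stop leaves frequency complete. In the equal-risk calculation about 31% to 33% of cough withdrawals stay in the frequency ANOVA, and some stay in the 4-way ANOVA.
- A reader might apply the correlation of 0.3 to the 14.9% and 19.3% exclusions and get shifts of 0.08 to 0.10 SD. Those fractions come from a model with equal risk for everyone, which has no person-level selection. The person-level version gives about 0.05 SD at most.
- A reader might infer that terminations will go unreported. The plan is silent on tabulation, and participants are closely monitored. Silence is a gap, not proof of non-reporting.
- Healthy adults on a regular diet, screened for dysphagia and its causes, may rarely cough. At the low end about 1 person in 50 is lost and the bias is negligible.
- A mixed model is not a cure. In a simulation with assumed values it left about half to all of the complete-case bias for amplitude and timing, and at most about half for frequency, with the sign reversed in one setting.

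None of this supplies the missing rule. The triggers are broad, each participant takes 24 boluses on flow, and no documented rate shows that withdrawals will be rare.

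**Conclusion.** The concern holds as a specification gap with possible, unquantified bias. Withdrawal is triggered partly by events the protocol attributes to HFNC, the named analyses ordinarily discard incomplete participants, and neither the use of partial data nor a count of terminations by flow is planned. Estimates could rest mainly on people who tolerated the flows.

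The size and direction of any bias cannot be derived from the documents. Under the assumptions shown, the loss runs from about one participant to roughly 15% to 19% of the sample, and the bias is about 0.01 to 0.05 SD if a tenth of people carry the risk and |rho| is 0.3. It is zero if withdrawal is unrelated to the flow effect. The case for acting rests on the low cost of the remedy, not on a demonstrated large bias.

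**What to change.** Leave the clinical termination rule unchanged. In Plans for Data Analysis:

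1. Analyse all data recorded before termination with linear mixed models with participant random effects: flow for frequency; flow, volume, viscosity, age and their planned interactions for amplitude and timing. Keep the complete-case ANOVAs as sensitivity analyses.
2. Compute frequency from a shortened recording as swallows divided by minutes observed.
3. Record the flow in force and the reason for each termination. Report terminations by flow and reason among those exposed to that flow, with 50 L/min (small prongs) shown separately from 60 L/min, and interpret the flow comparisons alongside these counts.
4. Add a sensitivity analysis in which unrecorded flows are assumed worse than observed.

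The cost is some analysis-plan wording, slightly more analysis work and two items noted per terminated session, with no extra participants or procedures. The mixed model removes only part of any bias if stopping depends on the unrecorded response, which is why items 3 and 4 are needed. If nobody is withdrawn, little changes.
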